3.2.3 Study duration

This study is from February, 2008 to January, 2038, or longer.

3.2.4 Sample size

This study is planned to recruit 100 thousand subjects, from all participant centers that cover the North, South, East and Western parts of China.

3.2.5 Study centers

There are 68 participating research centers for this study, including 26 provinces, cities or autonomous regions. Detailed information can be found in Appendix 12.

4. Evaluation criteria

4.1 Clinical evaluation

4.1.1 Demographic data

The demographic data at baseline should be filled in as completely as possible, including: date of birth, age, family address, contact information, education level. At follow-up period(s), if information is changed, they will be updated.

4.1.2 Current medical history

The detailed and objective current medical history must be filled out by the physicians. If case report form (CRF) cannot describe the symptoms and characteristics of the subject in detail, fill in the blanks.

Describe the specific manifestations of cognitive impairment, such as the specific manifestations of memory impairment (nearly/distant/ semantic forgetting); the specific manifestations of language barriers (difficulty in finding words, understanding, expressing, naming, writing, etc.); specific manifestations of disorientation (time, place, people, etc.); specific manifestations of personality and mental behavior (apathy, withdrawal, depression, agitation, wandering, abnormal sleep, antisocial behavior such as theft, etc.; the specific forms of hallucinations such as visual hallucinations, auditory hallucinations, etc.); manifestations of dyskinesia (such as ataxia, Parkinson-like dyskinesia, involuntary movements, etc.); implementation of dysfunction; spatial skills decline and other specific performance.

Physicians should describe the extent of decline in each cognitive domain, whether cognitive impairment affects the patient's daily ability and social function, and how it behaves.

4.1.3 Past history

According to the current internationally recognized diagnostic criteria, the previous illness of the subject is diagnosed or confirmed, and the presence or absence of the relevant disease, the time of diagnosis and the course of the disease are recorded in detail. Try to let the subject or family provide the hospital's medical record/diagnostic certificate, etc., or the investigator will retrieve the patient's past medical records for inspection and confirmation.

4.1.4 Medication situation

The subject's medication needs to be documented in detail, including the name of the medication for the treatment of cognitive impairment and other diseases, the frequency of administration, and the adherence of the medication. Try to have the subject present a

medical record, drug package or prescription.

4.1.5 Family history and family diagram drawing

For subjects with a family history, the investigator should investigate in detail the incidence of each member of the family, and generally investigate the three generations of relatives of the patient. For cognitive impairment and suspected cognitive impairment in the family, the disease should be recorded in detail (e.g. age of onset, first symptom, progression of disease, involvement of each cognitive domain, age of dementia, diagnosis and treatment, clinical consistency with the proband, etc.).

4.1.6 Physical examination

Physical examinations include general medical examinations and neurological examinations performed by senior neurologists.

4.2 Neuropsychological assessment (See Appendix 1-11 for details)

Investigators should strictly follow the guidelines and scoring criteria, be consistent with different subjects and avoid inducing subjects. Patience is encouraged to complete the subject and, if needed, a short break. Check as far as possible in an independent, quiet space, try to be one-on-one with the subject to avoid outside interference.

4.2.1 Mini-Mental State Examinations (MMSE) (80)

The MMSE is a brief, frequently used screening instrument for dementia. The MMSE scale evaluates the following seven aspects: time orientation, location orientation, immediate memory, attention and computation, delayed memory, language, and visual space. There are a total of 30 topics. The total score ranges from 0 to 30. The test scores are closely related to the educational level. Higher scores indicate better cognitive function.

4.2.2 Montreal Cognitive Assessment (MoCA) (81)

The MoCA is, similar to the MMSE, a brief cognitive assessment designed to detect cognitive dysfunction at the MCI stage. This scale has been shown to have adequate sensitivity and specificity in clinical settings to detect suspected MCI. The MoCA evaluates a variety of cognitive domains including attention, executive function, memory, language, visual space, orientation, and computational capacity. The total score is 30 points.

4.2.3 Neuropsychiatric Inventory Questionnaire (NPI-Q) (91)

NPI-Q is a well-validated evaluation tool. It evaluates neuropsychiatric symptoms in AD based on interviews with informed individuals, with relatively short visit time (<15 minutes). It assesses the presence and severity of 12 neuropsychiatric features, including delusions, hallucinations, agitation/aggression, depression/bad mood, anxiety, euphoria, apathy, disinhibition, irritability/emotional instability, abnormal motor behavior, sleep/nighttime behavior, appetite and eating disorders. At the same time, the severity of the symptoms (1-3 points), frequency (1-4 points), and the degree of distress of the caregiver (0-5 points) are evaluated.

4.2.4 Geriatric Depression Scale (GDS) (92)

The GDS is a self-report scale designed to screen for symptoms of depression in the elderly and to measure the self feeling of the elderly within a week. The scale has a total of 30 items, including the following symptoms: low mood, reduced activity, irritability, withdrawal of painful thoughts, negative scores of the past, present and future. The total score is 0-10 points, which is normal; 11-20 points, mild depression; 21-30 points, moderate to severe depression.

4.2.5 Modified Hachinski Ischemic Scale (m-HIS) (95)

The m-HIS can be used to identify VaD through clinical findings. It has a total of 8 items, and 12 points. The items include stepwise aggravation, complain of physical symptoms, emotional loss of control, hypertension history, which are scored 1 point each; acute onset, stroke history, neurological focal symptoms, nervous system focal signs, which are scored 2 points each. The total score is 0-12 points. The higher the evaluation score, the greater the possibility of VaD: those with a score of 4 or less are AD; those with a score of 7 or more are VaD.

4.2.6 World Health Organization University of California-Los Angeles, Auditory Verbal Learning Test (WHO-UCLA AVLT) (84)

AVLT is a list learning task for evaluating multiple cognitive parameters related to learning and memory. In each of the three learning trials, 15 unrelated nouns are spoken out by the tester at the speed of one word per second, and the subjects immediately recall the words freely, which is called the immediate recall test. In addition, after 30-minutes delay of completing the unrelated test, the subject again freely recall the original 15-words list, which is to test delayed recall. Then the tester reads 30 words (including 15 learned words and 15

interference options), and asks the subject to judge whether it is a learned word, and records the number of correct words, which is a delayed recognition test. The results are expressed as the number of nouns that are correctly recalled in each trial. The scale examines the ability to enter, store, extract, pay attention, and vocabulary of memory, and the score increases with increasing educational level.

4.2.7 Trail Making Test (TMT) A and B (86)

Part A of TMT consists of 25 circles, numbered 1 to 25, and the tester instructs the subject to draw lines as fast as possible in increasing numerical order. Part B is also composed of 25 circles, but these circles are white circles (1-12) and black circles (1-13). Subjects need to alternately connect circles of different colors in numerical order. The completion performance of the subject is determined based on the number of correctly completed lines and the time required to complete. Although both the part A and part B rely on visual motion and perceptual scanning skills, part B requires considerable cognitive flexibility to complete the black and white transition connection under time pressure.

4.2.8 Digit Span Test (Forward and Backward) (DST) (87)

The DST requires the subject to repeat a sequence of numbers that are read aloud by the examiner. In the forward test, the subjects must repeat the numbers in the same order; in the backward test, the numbers are repeated in opposite order. The length of the digits gradually increases from 3 to 10 digits in the forward test, and gradually increases from 2 to 8 digits in the backward test, and each digit length includes two tests. The test is terminated when both tests are incorrect. The maximum score of the forward test is 10 points and that of the reverse test is 8 points.

4.2.9 Boston Naming Test (BNT) (88)

This visual naming based scale shows 30 items. The objects in the picture are presented to the subject in a pattern of easily identifiable first and then not easily identifiable. If the subject encounters difficulties in naming the object, the examiner will provide a clue prompt or an option prompt. Record respectively the correct number of independent initial naming, clue naming, and option naming.

4.2.10 Activities of daily living (ADL) (93)

The ADL scale can evaluate the daily activities of the subject comprehensively, accurately and quickly. It consists of the physical life self-care scale and the instrumental ADL. There are 14 items, including two parts: first, the physical life self-care scale has a total of 6 items, including toilet, eating, dressing, grooming, walking and bathing; second, instrumental ADL has a total of 8 items, including call, shop, prepare meals, do housework, laundry, use transportation, take medicine and financing abilities. The higher the subject scores, the worse the ability of daily living.

4.2.11 Clinical Dementia Rating Scale (CDR) (83)

The CDR is a refinement of information that the doctor obtains through conversations with the patient and his/her family, and to assess the degree of impairment of the patient's cognitive function, and then to quickly assess the severity of the patient's condition. The assessment of cognitive domains consists of six items: memory, orientation, judgment and problem solving, work and social ability, family life and hobbies, and independent living ability. The judgment is in five levels, "normal CDR=0, suspected dementia CDR=0.5, mild dementia CDR=1, moderate dementia CDR=2, severe dementia CDR = 3". The CDR-SOB (CDR sum of box) total score is a simple sum of the scores of the six items. CDR sum of boxes adds up the 6 items, and the total score ranges from 0 to 18. As long as the score is greater than 0, the subject has at least one cognitive impairment. Generally, the change value of CDR sum of boxes can be used in clinical trials to obtain more accurate cognitive evaluation (117). CDR is a widely used measure of the severity of dementia.

5. Imaging examination

At each assessment, subjects will receive MRI, PET, and carotid ultrasound. PET imaging includes FDG-PET and amyloid PET scans.

5.1 Imaging equipment and qualifications

Xuanwu Hospital and each sub-center have advanced imaging equipment. Most centers have Siemens or GE full-body MRI scanner, and some centers have PET/MR integrated whole body scanner or PET scanner. Each center has the license for the use of radioactive drugs by the National Food and Drug Administration (fourth category) and has the qualification to prepare new drugs (tracers) for research and development.

5.2 MRI

MRI should be performed within 1 month before or after neuropsychological testing (with no new vascular disease events). All subjects should be checked for MRI contraindications before MRI scanning, such as the presence of metal implants in vivo. Remove active metal objects from the body before examination. After the subjects lie down, his right temple is used as a stereotactic marker, and the scan follows given directions. Three dimensional T1 weighted images of the whole brain were obtained. All subjects will undergo regular scan (T1WI, T2WI, FLAIR, DWI, MRA) and hippocampal phase scan (coronal T1-FLAIR sequence). Image acquisition is completed by radiology department of each center, stored and transmitted in DICOM format, and then image processing is carried out to obtain brain volume, cortex thickness and other indicators. Fazekas score and MTA score were obtained and used as location and quantitative indicators of white matter lesions and gray matter atrophy.

5.3 PET

5.3.1 FDG-PET

FDG-PET can detect abnormal brain metabolism in patients with dementia, and should be performed within 1 month before or after neuropsychological examination (with no new vascular disease event). Fasting for at least 6 hours before examination, and fasting blood glucose was measured. Blood glucose levels should be <140 mg / dL (7.8 mmol/L). Image acquisition is completed by radiology department of each center, stored and transmitted in DICOM format, and then image processing is carried out to obtain whole brain and regional standard uptake value ratio (SUVR), and used as location and quantitative indicators of brain metabolic function.

5.3.2 ¹¹C-PIB PET

Amyloid tracer [N-methyl-¹¹C]2-[4'-(methylamino) phenyl]-6-hydroxybenzothiazole (¹¹C-PIB) is the mostly studied and relatively mature Phenothiazine Aβ imaging agent, which is a ¹¹C-labeled derivatives of Thioflavin-T. It can specifically bind to Aβ plaques in the brain of AD patients and is used for positioning and quantitative analysis of Aβ in brain. ¹¹C-PIB PET can differentiate AD and normal patients in the early and middle stages of the disease, reflect the pathological changes of brain tissue, provide more objective data for early diagnosis. Further combined with clinical history, laboratory tests, neuropsychology scale and structural imaging results, it can help improve the accuracy of the diagnosis to guide early treatment. Image acquisition is completed by radiology department of each center, stored and transmitted in DICOM format, and then image processing is carried out to obtain whole brain and regional standard uptake value ratio (SUVR), and used as location and quantitative indicators of Aβ deposition.

5.4 Carotid ultrasound

Carotid ultrasound can clearly demonstrate the vascular intima-media thickness, the location and size of plaque, the degree of vascular stenosis, and analyze hemodynamics. It plays a key role in the assessment and diagnosis of vascular-related diseases caused by atherosclerosis. Carotid ultrasound examination should be performed within 1 month before or after neuropsychological examination (with no new vascular disease event). An experienced ultrasound physician is required to perform the operation according to "Guidelines for Carotid Ultrasound Examination". Longitudinal and transverse section scanning are performed from frontal and lateral directions. Observe and record the peak systolic velocity (PSV), end diastolic velocity (EDV), intima-media thickness (IMT) and plaque (diameter, number, acoustic properties) of internal carotid artery, common carotid artery and carotid bifurcation.

6. Laboratory examination

6.1 Laboratory testing items

6.1.1 Genetic gene detection

PS1, PS2, APP, APOE and other genetic gene tests are performed on cognitive normal and dementia individuals in ADAD cohort and unknown mutation cohort. Collect the genetic information and biological materials of familiar dementia pedigree to help the basic and clinical research for the pathogenesis of dementia.

6.1.2 Risk gene locus detection

Conduct whole-exon analysis, genome-wide analysis, whole genome association analysis for each enrolled participant, using case-control methods to detect, study and analyze novel risk gene loci that are disease relevant. Explore new pathogenic genes, mechanisms, and risk pathways to provide genetic basis for disease prevention and control.

6.1.3 Body fluid biomarkers detection

Conduct biomarkers detection in cerebrospinal fluid, blood, urine and saliva for each enrolled group, including blood and urine

routine tests, biochemistry, electrolytes and coagulation function tests, cerebrospinal fluid routine and biochemistry tests, etc. Special items include $A\beta40$, $A\beta42$, t-tau, p-tau and neurogranin in cerebrospinal fluid and blood to study and explore early diagnostic biomarkers and risk predictors of disease progression.

6.2 Collection and storage of biological specimens

6.2.1 Blood sample

Each participant requires fasting blood collection in the morning and 8ml of peripheral blood is drawn. 5ml is injected into purple head anticoagulation tube, and 3ml is injected into red head non-anticoagulated tube. Name and number are signed on each blood collection tube. Centrifuge within 2 hours. After the purple head anticoagulation tube is centrifuged at 2000 rpm for 10 minutes, aspirate upper layer plasma by pipette and retain the remaining blood sample in the tube. After the red head non-anticoagulation tube is centrifuged at 2000 rpm for 10 minutes, the serum is pipetted and distributed into two of 1.5ml centrifugal tubes, about 500µl per tube. Name, number and the type of specimen are signed on each centrifugal tube (serum is labeled Q, while plasma is J). Centrifugal tubes are immediately stored at -80°C, while the anticoagulation tubes are stored at -20°C fridge.

6.2.2 Cerebrospinal fluid sample

Lumbar puncture should be done in the morning. To eliminate the impact of puncture bleeding on the quality of cerebrospinal fluid specimens, the first 1-2 ml of CSF should be discarded. 10ml CSF for biomarker analysis should be collected. Centrifuge within 2 hours after collection (2000 rpm for 10 minutes), then pipette and distribute the supernatant into ten of 1.5ml centrifugal tubes, 1 ml per tube. Centrifugal tubes are immediately stored at a -80°C fridge.

7. Informed consent

In this study, a series of memory and intelligence tests will be performed on participants, and if necessary, auxiliary examination will be arranged to confirm the diagnosis. After that, regular follow-up will be arranged for each person to tract the change of disease status. Participants and their families should be informed that they should sign an informed consent form after fully understanding the research, and should be reminded that participation in the study is voluntary.

According to the current edition of the Declaration of Helsinki, the principle of informed consent will be implemented before protocol procedures are carried out. Information about the research content should be provided in both oral and written form and reviewed by an ethics committee. Subjects, relatives and guardians must have ample opportunity to inquire about details of the study. The informed consent should be in the language and script that subjects or legal representative can fully understand. During the clinical study, subjects can keep abreast of their research information.

Informed consent will be recorded by using a written document approved by the Ethics Committee and signed by the subject and/or legally authorized representative. The written informed consent document will embody the elements of informed consent as stated in the Helsinki Declaration and will comply with local regulations. Informed consent should mainly include the following contents:

7.1 Inform benefits and risks

7.1.1 Benefits

This study can help clinicians understand patient's disease and enable participants to obtain good and free medical services, such as free neuropsychological assessment, neurology physical examination, as well as follow-up observation and consultation.

7.1.2 Risk

The entire research process may occupy a certain period of time of the participants, but will not cause any physical harm.

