3.2 Research methods

Through the establishment of a national multi-center cognition and aging cohort, this study will collect relevant demographic information and clinical data, biofluid samples, neuropsychological evaluation, imaging examination, blood examination and other comprehensive evaluation of study subjects, so as to study the epidemiology, influence factors, genetics and pathogenesis, diagnostic standards, prevention and control strategies of dementia and its subtypes. The study flow chart is as follows (figure 1):

3.2.1 Inclusion and exclusion criteria:

Community population: age ≥ 55 years, male or female, with consent to participant the study.

Hospital population: subjects are all over 18 years old. Through clinical evaluation, neuropsychological test, imaging examination, blood and cerebrospinal fluid examination, etc, we will comprehensively evaluate the cognitive function and various test measures.

(1) MCI and its subtypes

Inclusion criteria:

- 1) Diagnosis according to 2004 Peterson's MCI criteria.
- 2) CDR = 0.5.
- 3) Memory loss is prominent, and may also be with other cognitive domain dysfunction.
- 4) Insidious onset, slow progress.
- 5) Not reaching the level of dementia.

Exclusion criteria:

- 1) With history of stroke and a neurological focal sign, the imaging findings are consistent with cerebral small vessal disease (Fazekas score ≥ 2 points).
- 2) Other neurological diseases that can cause brain dysfunction (such as depression, brain tumor, Parkinson's disease, metabolic encephalopathy, encephalitis, multiple sclerosis, epilepsy, brain trauma, normal intracranial pressure hydrocephalus, etc.).
- 3) Other systemic diseases that can cause cognitive impairment (such as liver, renal and thyroid insufficiency, severe anemia, folic acid or vitamin B12 deficiency, syphilis, HIV infection, alcohol and drug abuse, etc.).
 - 4) Mental and neurodevelopmental retardation.
 - 5) Contraindications to MRI.
 - 6) Suffering from a disease that cannot be combined with cognitive examination.
 - 7) Refuse to draw blood.
 - 8) Refuse to sign the informed consent at baseline

(2) Sporadic Alzheimer's disease (SAD)

Inclusion criteria:

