8.2 Lumbar puncture

The participants may have local discomfort at the lumbar puncture site, as well as back pain, neck stiffness and shoulder pain. The puncture site may appear bruising, swelling or rash, and the dizziness or headache may occur for the participants after lumbar puncture. The risk of other related complications is very rare, including the infections of puncture site, allergies to local anesthetics or disinfectants, and the injury of spinal nerve.

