8.3 Blood collection

Slight discomfort, bruising, bleeding or infection at the venipuncture site. Very few participants may faint during or after the puncture.

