8.4 Imaging

Participants may be allergic to the contrast agent or have radioactive substance radiation exposure risk during the MRI or PET inspection. Participants with metal implants may experience implant displacement during exposure to magnetic fields. Claustrophobia and anxiety may occur on the participants for lying in enclosed spaces.

9. Ethics

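### The consent content in section 7.1.2 denies any physical harm, yet every participant gives blood and sections 8.2 to 8.4 list physical harms of study procedures

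*Protocol*

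**What the plan says.** The introduction to section 7 (Informed consent) closes with "Informed consent should mainly include the following contents", and sections 7.1 to 7.4 follow as that content. The only text under 7.1.2 (Risk) is: "The entire research process may occupy a certain period of time of the participants, but will not cause any physical harm".

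Other sections describe the procedures and their risks:

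- **Blood.** Section 6.2.1: "Each participant requires fasting blood collection in the morning and 8ml of peripheral blood is drawn". Section 8.3 gives the risks: "Slight discomfort, bruising, bleeding or infection at the venipuncture site. Very few participants may faint during or after the puncture".
- **Lumbar puncture.** Section 6.2.2 describes the collection of 10 ml of CSF. Section 8.2 lists local symptoms, pain, dizziness and headache, and then, as very rare complications, "the infections of puncture site, allergies to local anesthetics or disinfectants, and the injury of spinal nerve".
- **Imaging.** The opening of section 5: "At each assessment, subjects will receive MRI, PET, and carotid ultrasound". Section 8.4 says that participants may react to contrast agent or "have radioactive substance radiation exposure risk during the MRI or PET inspection", and that metal implants may be displaced.

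**The concern.** The protocol carries two risk statements that cannot both be true. The false one stands where the authors of consent forms are told to look. Section 8, which has the accurate list, is not named as consent content.

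The stake is what participants are told before they agree. A unit that builds its form from section 7.1.2 would deny any physical risk from procedures for which the protocol itself lists harms. Those signing include people with dementia who consent through a guardian, and normal controls from age 18. An ethics committee reviewing a form against the protocol could find support for either statement.

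**Working it through.** No formula applies, and the protocol gives no figure to reproduce. The check sets the passages side by side.

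**Step 1. Scope of the no-harm statement.** Its subject is the research process in its entirety. It is not limited to the neuropsychological tests or to any group.

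**Step 2. Is any procedure with listed physical harms required of everyone?** One such procedure is enough to make the statement false.

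| Procedure | Who undergoes it, according to the protocol | Physical risks listed |
|---|---|---|
| Blood collection | Each participant (6.2.1) | 8.3 |
| Lumbar puncture | Described as a study procedure (6.1.3, 6.2.2), not clearly mandatory | 8.2 |
| MRI and PET | At each assessment (5), though only some centers have PET (5.1) | 8.4 |

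Blood collection meets the condition. Two other places agree with 6.2.1: section 6.1.2 plans genomic analysis for every enrolled participant, and Table 1 in section 3.2.2 marks laboratory examination at baseline and follow-up. In section 3.2.1, "Refuse to draw blood" is an exclusion criterion for MCI, sporadic AD, VaD and normal controls, which is 4 of the 5 hospital groups. It is not listed for familial AD. Refusal of lumbar puncture is an exclusion in none of the five.

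**Step 3. Count of physical risks named.**

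- 8.2: local discomfort, back pain, neck stiffness, shoulder pain, bruising, swelling, rash, dizziness, headache, infection, allergy, spinal nerve injury = 12
- 8.3: discomfort, bruising, bleeding, infection, fainting = 5
- 8.4: contrast allergy, radiation exposure, implant displacement = 3

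Total: 12 + 5 + 3 = 20, against 0 in section 7.1.2. Claustrophobia and anxiety (8.4) and the burdens of testing (8.1) are left out as not physical.

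**Step 4. Does any text reconcile the two?** None does. Section 7.3, itself consent content, provides for the case of a potential health risk to participants, and section 3.2.2(5) lists safety risks among the reasons for termination. Both presuppose risk and so add to the conflict with 7.1.2.

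**The case against.** The contradiction itself is hard to dispute. The case on the other side concerns its reach and weight.

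- **Reach.** That every participant gives blood rests chiefly on one sentence in a specimen-handling section. Section 3.2.1 attaches blood and CSF examination to the hospital population and asks of the community population only age 55 or over and consent. Section 7 opens with memory and intelligence tests, with further examination if needed. The split of the 100 thousand between community and hospital is not given. This deserves mention, but 6.2.1 is worded without exception, and 6.1.2 and Table 1 support it. Even if blood were drawn only in the hospital groups, 7.1.2 would still be false for them.
- **The count.** The 20 items are a tally of words. Bruising, infection and allergy recur across procedures, radiation is an exposure rather than an event, and the section 3.2.1 exclusions and the pre-scan check in section 5.2 reduce the implant risk. Section 8 calls the serious lumbar puncture complications very rare. This stands: the tally shows the extent of the conflict in the text and says nothing about frequency or severity.
- **Consequence.** The list of consent content is introduced as the main content, so it need not be exhaustive. Sections 7 and 9.2 require the Helsinki elements, and sections 9.1 and 9.1.4 require ethical review of each unit and approval of its consent statement. Some forms may therefore already list the section 8 risks. This also stands, but a form that adds those risks to a denial of physical harm would still contradict itself.

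**Conclusion.** The concern holds and must be fixed. Section 7.1.2 is false as written, because blood collection alone carries physical risks that section 8.3 lists. Lumbar puncture and imaging widen the conflict, but the conclusion does not depend on them.

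Taking section 6.2.1 at its word, the contradiction covers all 100 thousand planned subjects. How many undergo lumbar puncture or PET, and how many scans each has, cannot be derived from the protocol. Nor can it be established here whether any participant was given the no-harm wording, since the consent forms are not available. The finding concerns the content that the protocol prescribes for consent. It does not bear on any endpoint or analysis.

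**What to change.** Delete the no-harm clause from section 7.1.2. In its place put the risks already written in sections 8.1 to 8.4, by procedure, for the procedures that each group undergoes, so that sections 7 and 8 agree.

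The sponsor should then check the consent forms in use at the participating units (section 3.2.5 gives 68 centers) for the no-harm wording. Only where a form repeats it should that form be corrected and the participants concerned be informed through the ethics committee.

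The cost is a wording change to the protocol and any affected forms, an ethics amendment and the check of the forms. No procedure is added. Franker wording might slightly lower uptake of lumbar puncture or PET; the protocol gives no basis for estimating this.
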